## 1. OBJECTIVES

This is a pilot study to explore the clinical activity of Eribulin Mesylate (HALAVEN, hereafter referred to as Eribulin) as a single agent for the treatment of patients with metastatic or unresectable angiosarcoma or Epithelioid hemangioendothelioma (EHE). We hypothesize that Eribulin will lead to objective responses and/or durable disease control in patients with angiosarcoma or EHE.

### 1.1 Study Design

We propose a single arm, single stage pilot study to explore the clinical activity of Eribulin in angiosarcoma and EHE with the primary objective of Overall Response Rate (ORR, PR+CR) by RECIST 1.1.

Patients will receive Eribulin on day 1 and day 8 of a 21-day cycle.

Imaging will be obtained every 6 weeks for the first 7 cycles (before C3, C5 and C7) and then every 9 weeks for C7 onwards (C10, C13, etc.).

### 1.2 Primary Objectives

- To determine the Objective response rate (ORR, partial response [PR]+complete response [CR]) by RECIST 1.1 of angiosarcoma/EHE patients treated with Eribulin

### 1.3 Secondary Objectives

- To further characterize the clinical activity of Eribulin in this population by:
  - Progression-Free Survival (PFS)
  - Disease Control Rate (DCR = ORR + Stable Disease [SD] at 24 weeks)
- To further characterize the safety profile of Eribulin in this patient population

### 1.4 Exploratory Objectives

- To determine any correlation between angiosarcoma or sarcoma subtype and response
- To determine any correlation between response and genomic characterization of the sarcoma
- To determine genomic and expression profile changes, via biopsy samples and/or circulating free DNA exome sequencing, over time after treatment with Eribulin

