## 2. BACKGROUND

### 2.1 Study Disease(s)

The sarcomas are a heterogeneous family of mesenchymal malignancies arising in bone or soft tissue. For patients with metastatic soft tissue sarcoma (STS), single agent or combination chemotherapy has led to a median survival of only 12 months across all histologies.(1, 2) Angiosarcoma (AS) is an uncommon STS that can arise in nearly any organ including the head and neck, breast, extremities, trunk, liver and bone. There is a peak incidence in the 7th decade of life.(3) The cause for most AS is unknown with subsets linked to exposure to radiation, foreign materials, toxins (e.g. vinyl chloride), chronic inflammation or lymphedema (Stewart-Treves syndrome) and genetic syndromes (e.g. BRCA1, NF1, Maffucci's).(4)

Multimodality therapy, including surgery, radiation and standard chemotherapy agents including taxanes and anthracyclines, is the treatment backbone of this disease. There is ongoing research into the role of VEGF-directed therapies and tyrosine kinase inhibitors. However, despite this, angiosarcomas are extremely aggressive tumors with stage for stage worse survival than other STS. For example in one series half of patients had died by 11 months.(5)

Epithelioid hemangioendothelioma (EHE) is a rare vascular sarcoma with a variable clinical course.(3) EHE can develop in virtually any organ and it frequently metastasizes to the lung and liver. Most EHE is typically genetically characterized by the gene fusion WWTR1-CAMTA1. There are no treatments for EHE and where metastatic mortality remains high.

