## **2.4 Correlative Studies Background**

In this pilot study, we seek to determine if there are expression and/or genomic variations that correlate with mechanisms of response and/or resistance to Eribulin as a single agent in patients with metastatic or unresectable angiosarcoma. Tumor samples from core needle biopsies pre- and post-treatment will be analyzed by RNA seq and whole exome sequencing. Whole exome sequencing from cell free DNA (cfDNA) will be analyzed from peripheral blood from angiosarcoma patients.

The Broad Institute has sequenced exomes or genomes of over 5000 tumors and has also pursued RNA-seq in hundreds of tumors to discover gene fusions, splice isoforms, and mutations. The Institute has extensive experience in the application of genomics to studies of cancer drug response and resistance in multiple cancer types (Wagle, Emery et al, Journal of Clinical Oncology 2011(25); Van Allen, Wagle, et al, Cancer Discovery, 2014a(26); Wagle, Van Allen, et al, Cancer Discovery, 2014b; Wagle et al, Cancer Discovery, 2014c; Wagle et al, New England Journal of Medicine, 2014(27)). In addition, Broad teams have experience performing sequencing from small amounts of starting material. The Broad Institute now routinely generates WES and RNA-seq data using DNA/RNA obtained from a single core biopsy.

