### **3. PARTICIPANT SELECTION**

#### **3.1 Eligibility Criteria**

- 3.1.1 Metastatic or locally advanced angiosarcoma, treated with at least one prior systemic therapy where no standard of care curable therapy is available OR metastatic or locally advanced malignant and progressive epithelioid hemangioendothelioma (EHE).
  - 3.1.1.1 A maximum of 5 EHE patients will be accrued on this study
- 3.1.2 Archival tissue confirming the diagnosis must be reviewed by BWH/DFCI/MGH pathology.
- 3.1.3 Progression on at least one prior systemic therapy or progression during an observation phase of no anti-cancer therapy within the prior 3 months; prior taxanes are allowed

3.1.4 Participants must have measurable disease by RECIST 1.1, defined as at least one lesion that can be accurately measured in at least one dimension (longest diameter to be recorded for non-nodal lesions and short axis for nodal lesions) as  $\geq 20$  mm with conventional techniques or as  $\geq 10$  mm with spiral CT scan, MRI, or calipers by clinical exam. See Section 11 for the evaluation of measurable disease.

3.1.5 Age  $\geq 18$  years.

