### **9.2.2 Sarcoma whole exome (WES) and transcriptome sequencing (RNA Seq)**

- 9.2.2.1 Core or excisional biopsies will be performed 1. After registration but before C1D1 and 2. Prior to the first imaging and C3D1
- 9.2.2.2 Handling of Specimens(s): Specimens will be divided either at the bedside or in the frozen laboratory by pathology for correlative studies and submission to the MGH or BWH pathology. Research samples will be placed in 2 mL cryovials and packaged for shipping on dry ice.
- 9.2.2.3 Shipping of Specimen(s): Research specimens will be couriered to the Broad Institute immediately after processing.
- 9.2.2.4 Site(s) Performing Correlative Study: Analysis of DNA by WES will be performed at the Broad Institute
- 9.2.2.5 Methods: Our approach will characterize specimen “sets” consisting of pre-treatment and, when applicable, post-treatment tumor samples from each patient. Genomic DNA and polyadenylated RNA will be extracted from tumor using standard techniques, and WES and RNA-seq will be performed by the Broad Institute Genomics Platform. The exome will be selected using solution-phase hybrid capture(35-38) and sequencing will be performed using the Illumina HiSeq2500, yielding an average depth of coverage of >150-fold. WES data will be analyzed for base substitutions, small insertions/deletions, and copy number alterations(30-34). For RNA-seq, strand-specific cDNA libraries will be generated, and Illumina sequencing libraries will be prepared following established protocols. Each sample will be sequenced with an Illumina HiSeq2500. RNA-seq data will be analyzed for fusions, chimeric read-through transcripts, point mutations, and instances of alternative splicing. RNA-seq data will also be used to determine gene expression levels. Data from RNA-seq will be combined with the WES results to nominate candidate genomic alterations. Differences in genomic alterations between pre- and post-treatment tissues will be analyzed by algorithms described below.

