## **13. STATISTICAL CONSIDERATIONS**

### **13.1 Study Design/Endpoints**

This is a pilot phase II clinical trial with a primary endpoint of objective response per RECIST 1.1 among patients with metastatic or unresectable angiosarcoma and EHE treated with Eribulin.

For the primary endpoint of best overall objective response with a null hypothesis of 10% and an alternative hypothesis of 35%, we would need 16 patients in a single-stage design. We will need to observe at least 4 responses out of 16 patients to accept the treatment. The power for this design is 87% using the exact binomial distribution. The operating characteristics of this design are calculated using one-sided 10% type I error.

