### **13.5 Analysis of Secondary Endpoints**

There is at least 74% probability of observing one or more rare (8% true probability) events, and 93% probability of observing toxicities that have a true occurrence of at least 15%. With 16 treated patients, the maximum width of a 90% two-sided exact binomial confidence interval for any estimated adverse event proportion will be no wider than  $\pm 22\%$ .

Progression-free survival will also be calculated. Progression-free survival, will be defined as the duration of time from start of treatment to time of progression or death, whichever occurs first and will be estimated using the Kaplan-Meier method. The disease control rate (Complete Response, Partial Response, and Stable Disease) at 24 weeks will also be calculated using the exact binomial distribution and 95% confidence interval.

We will explore the relationship between integrated biomarkers detected by cfDNA exome sequencing, WES, RNAseq expression profiling and response to Eribulin. We will use Fisher's Exact Test to assess the relationship between each biomarker and response to eribulin assuming a best overall objective response of 35%. Biomarkers may be continuous or binary. For example, with this design, assuming tissue is available on 100% of the sample, the probability of concluding eribulin response is related to the exploratory biomarker is 82%; given the unknown true response is 70% and 4% in positive marker versus negative marker patients, respectively, assuming 50% of the population is over-expressed for the biomarker or the biomarker is continuous and split at the median. The operating characteristics of this design are calculated using a two-sided exact test with 10% type I error.

We will explore the relationship between changes in the integrated biomarkers from baseline to cycle 3 due to eribulin treatment using a paired t-test. With 16 patients, we will have 81% power to detect an effect size of 0.67 using a paired t-test with a 0.1 two-sided significance level.

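### The biomarker–response tests in section 13.5 pool angiosarcoma and EHE without a within-histology result, so a marker that only labels histology can be declared related to response

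*Combined protocol and SAP*

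**What the plan says.** Section 1.4 lists the exploratory aim: "To determine any correlation between response and genomic characterization of the sarcoma". Section 13.5 sets the method: "We will use Fisher's Exact Test to assess the relationship between each biomarker and response to eribulin". The test is two-sided at 10%. The power example assumes tissue from every patient, half of them marker-positive, and response of 70% versus 4%, and it states 82%. No stratification, adjustment or angiosarcoma-only analysis is named.

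The sample is mixed. Section 13.1 says "we would need 16 patients in a single-stage design", and item 3.1.1.1 says "A maximum of 5 EHE patients will be accrued on this study". If 16 enrol, at least 16 − 5 = 11 have angiosarcoma.

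One histology has its own genomic signature. Section 2.1 says "Most EHE is typically genetically characterized by the gene fusion WWTR1-CAMTA1", and section 9.2.2 says "RNA-seq data will be analyzed for fusions, chimeric read-through transcripts, point mutations, and instances of alternative splicing". A near-label for EHE is therefore among the things measured.

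The correlative population is worded in three ways. Section 2.4 looks for variations that "correlate with mechanisms of response and/or resistance to Eribulin as a single agent in patients with metastatic or unresectable angiosarcoma", which names angiosarcoma alone. Section 9.1 speaks of both angiosarcoma and EHE. The figures in section 13.5 use all 16 patients.

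**The concern.** When two diseases share one 2×2 table, any marker distributed unevenly between them picks up the difference in their response rates. The result can be significant although, within angiosarcoma and within EHE, marker-positive and marker-negative patients respond alike. This is confounding by histology. The Benjamini–Hochberg step in section 9.2.3 concerns recurrent alterations and would not remove it.

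An exploratory screen exists to choose which leads to pursue. If the leading markers mainly tell EHE from angiosarcoma, the screen has rediscovered the diagnosis, and the report as planned would not show that.

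**Working it through.** **Inputs from the documents.** n = 16 (13.1); at most 5 EHE (3.1.1.1); Fisher's exact test, two-sided 10%, 70% versus 4%, half marker-positive, stated power 82% (13.5); paired t-test, effect size 0.67, two-sided 10%, stated power 81% (13.5).

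**Assumed.** Response rates by histology. The documents give only the pooled 10% null and 35% alternative, so a range is shown.

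**Formula.** For groups of n1 and n2 with response rates p1 and p2,

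P(declare) = Σx Σy Bin(x; n1, p1) · Bin(y; n2, p2) · 1[Fisher p(x, y) ≤ 0.10].

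**Step 1: the plan's own figure.** With n1 = n2 = 8, p1 = 0.70 and p2 = 0.04, the sum is 82.1%, against 82% stated. This is a single table holding all 16 patients, which confirms the pooling.

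**Step 2: a marker identical to histology, with no effect within either disease.** Take EHE versus angiosarcoma as the two groups. With 5 and 11 patients, 0/5 versus 6/11 gives p = 0.093 and 4/5 versus 2/11 gives p = 0.036; both are declared. As a hand check, if EHE never responds, the test declares exactly when at least 6 of 11 angiosarcoma patients respond. At 45% that is P(Bin(11, 0.45) ≥ 6) = 36.7%.

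| EHE / angiosarcoma response | 5 EHE | 3 EHE | 2 EHE |
|---|---|---|---|
| 35% / 35% | 4.6% | 3.2% | 2.7% |
| 25% / 35% | 4.8% | – | – |
| 20% / 35% | 5.6% | – | – |
| 20% / 40% | 8.7% | – | – |
| 10% / 40% | 14.8% | 2.4% | 0.4% |
| 0% / 45% | 36.7% | 7.0% | 1.1% |
| 60% / 20% | 36.8% | 29.6% | 25.1% |
| 70% / 20% | 49.9% | 41.2% | 34.2% |

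**Step 3: a marker that tags histology only in part.** Take a median split whose high half holds all 5 EHE and 3 angiosarcoma patients. Pooled Fisher declares it 2.8% of the time at 35%/35%, 4.6% at 20%/40%, 7.2% at 10%/40%, 12.9% at 0%/45%, 11.5% at 60%/20% and 16.4% at 70%/20%.

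**Step 4: the stratified alternative.** Let T be the number of marker-positive responders summed over the two histologies. Given each stratum's margins, T is a sum of independent hypergeometric counts. The two-sided p adds the probabilities of all values no likelier than the one observed. A pure histology label has no within-stratum contrast, so it is declared 0% of the time. The split in Step 3 is declared 2–4% of the time.

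**Step 5: what stratifying does to power.** Use the plan's 70% versus 4% with 8 of 16 patients marker-positive, 5 EHE and 11 angiosarcoma:

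| Marker-positive EHE + angiosarcoma | Stratified power |
|---|---|
| 0 + 8 | 49.5% |
| 1 + 7 | 81.4% |
| 2 + 6 | 87.1% |
| 3 + 5 | 85.1% |
| 4 + 4 | 83.5% |
| 5 + 3 | 66.0% |

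Pooled Fisher gives 82.1%.

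**Step 6: if the population is angiosarcoma only, with 11 patients.** Fisher power at 70% versus 4% is 68.0% with 6 marker-positive and 76.2% with 5. For the paired t-test, the noncentral t with noncentrality 0.67·√n gives 81.9% at n = 16 (stated 81%) and 66.4% at n = 11.

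**The case against.** The strongest reply is that a pooled test answers a legitimate question. Section 13.5 speaks of response being related to a biomarker and section 1.4 of correlation. If EHE and angiosarcoma truly respond differently, a fusion that marks EHE is related to response among the patients enrolled, and rejecting that marginal null is no type I error. Section 9.1 supports a mixed correlative population. Section 1.4 also lists histological subtype versus response as a separate aim, and section 2.1 already names the EHE fusion, so few readers would mistake that fusion for a discovery.

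Much of this stands. A reader might infer that the plan would announce such markers as predictors of eribulin response; its wording does not go that far, and a single-arm trial could not separate predictive from prognostic markers under either test. A reader might also infer that false leads are likely. That depends on unknown rates: with 5 EHE patients and gaps of 10–20 points (EHE lower), a pure label is declared less often than the nominal 10%. Five EHE patients is a cap, not a forecast. Nor do the documents say how far expression differs between the two diseases.

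What remains is that section 13 gives no method for the subtype aim and does not connect it to the biomarker tests. The pooled result alone cannot show whether an association exists within either disease, and less familiar markers than the known fusion carry no warning label.

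**Conclusion.** The concern holds as a gap in an exploratory analysis. With 5 EHE and 11 angiosarcoma patients, a pure histology label is declared 4.6% of the time at equal 35% rates, 5–9% at gaps of 10–20 points with EHE lower, 15% at 10% versus 40%, 37% at 0% versus 45%, and 37–50% at 60–70% versus 20%. With 2 or 3 EHE patients the figures are 0.4–7% at 10% versus 40% and 0% versus 45%, but 25–41% if EHE responds much better. A partly tagging median split is declared 3–16% of the time. All the unequal rates are assumptions.

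It would be tempting to conclude that the pooled test should be replaced because stratifying costs nothing. The calculations do not support that: stratified power is 81–87% when the marker occurs in both histologies, but 66% if all 5 EHE patients are marker-positive and about 50% if none are. The histology-adjusted result belongs beside the pooled test.

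The inconsistent correlative population needs correcting whatever the response rates. The primary endpoint and its 4-of-16 rule are unaffected.

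**What to change.** In section 13.5:

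- Keep the pooled Fisher test as the marginal screen.
- For every marker, also report an exact conditional test stratified by histology (angiosarcoma versus EHE) and the angiosarcoma-only result.
- Describe a marker as related to response beyond histology only if the within-histology result supports it.
- Report markers that do not vary within a histology, such as WWTR1-CAMTA1, as histology differences.

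Make sections 2.4, 9.1 and 13.5 name the same correlative population. If it is angiosarcoma only, restate power for as few as 11 patients: 68–76% instead of 82% for the response test, and 66% instead of 81% for the paired t-test.

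The cost is wording and a few more table columns. Histology is established at eligibility, so no patients, visits or data are added. The downside is the weaker stratified power for markers concentrated in one histology, and this should be stated with the method.

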## 2. BACKGROUND

### 2.1 Study Disease(s)

The sarcomas are a heterogeneous family of mesenchymal malignancies arising in bone or soft tissue. For patients with metastatic soft tissue sarcoma (STS), single agent or combination chemotherapy has led to a median survival of only 12 months across all histologies.(1, 2) Angiosarcoma (AS) is an uncommon STS that can arise in nearly any organ including the head and neck, breast, extremities, trunk, liver and bone. There is a peak incidence in the 7th decade of life.(3) The cause for most AS is unknown with subsets linked to exposure to radiation, foreign materials, toxins (e.g. vinyl chloride), chronic inflammation or lymphedema (Stewart-Treves syndrome) and genetic syndromes (e.g. BRCA1, NF1, Maffucci's).(4)

Multimodality therapy, including surgery, radiation and standard chemotherapy agents including taxanes and anthracyclines, is the treatment backbone of this disease. There is ongoing research into the role of VEGF-directed therapies and tyrosine kinase inhibitors. However, despite this, angiosarcomas are extremely aggressive tumors with stage for stage worse survival than other STS. For example in one series half of patients had died by 11 months.(5)

Epithelioid hemangioendothelioma (EHE) is a rare vascular sarcoma with a variable clinical course.(3) EHE can develop in virtually any organ and it frequently metastasizes to the lung and liver. Most EHE is typically genetically characterized by the gene fusion WWTR1-CAMTA1. There are no treatments for EHE and where metastatic mortality remains high.

## 2.2 Study Agent

### 2.2.1 Eribulin

Eribulin mesylate (HALAVEN®) is a synthetic analog of halichondrin B (HalB), a natural product isolated from the marine sponge *Halichondria okadai*. HalB is a large polyether macrolide that exerts potent anti-cancer effects in cell-based and animal models of cancer.(6-8) The structurally simplified synthetic analog Eribulin mesylate has shown potent anti-cancer properties in preclinical models.(8)

### 2.2.2 Therapeutic Pathway

Results of *in vitro* studies demonstrate that eribulin inhibits cell growth with sub- to low-nmol/L half-maximal inhibitory concentration (IC50) values in a wide range of established human cancer cell lines, including breast, colon, prostate, ovarian, small cell and non-small cell lung cancer, as well as histiocytic lymphoma, promyelocytic leukemia, pharyngeal squamous cell carcinoma (head and neck cancer), melanoma, and uterine sarcoma. Eribulin exerts its anti-cancer effects via a tubulin-based antimitotic mechanism, leading to G2/M (GAP 2/mitosis stages of cell cycle)

cell cycle blocks, disruption of mitotic spindles, and ultimately apoptotic cell death after prolonged mitotic blockage.

Eribulin is mechanistically distinct as an inhibitor of microtubule dynamics, leading to inhibition of microtubule growth in the absence of effects on microtubule shortening, and formation of non-productive tubulin aggregates. This pattern of inhibitory effects on microtubule dynamics is not shared by known tubulin-targeted agents.(9)

Eribulin may have additional effects on tumor vascular remodeling and reversal of EMT. It has been reported that the abnormal vasculature present in tumors impairs blood perfusion and oxygenation, leading to hypoxic conditions, which promotes invasion, metastasis, and overall aggressiveness of tumor cells through epithelial mesenchymal transition (EMT)-related processes. Normalization of vascular perfusion is therefore gaining interest as a therapeutic approach to inhibit motility, invasiveness, and aggressiveness of tumor cells.

Preclinical data suggest that eribulin mesylate improves tumor blood perfusion through vascular remodeling, which may indirectly contribute to reduced metastasis, invasion, and reversal of EMT in the tumor microenvironment, leading to a normoxic tumor microenvironment.(10-13)

### 2.2.3 Clinical Experience with Eribulin

Nine Phase 1 clinical studies have been completed with eribulin. The National Cancer Institute (NCI)-sponsored two Phase 1 studies of eribulin: NCI Study 5730 and NCI Study 7444. Eisai has sponsored seven studies: E7389-A001-101, E7389-A001-102, E7389-E044-103, E7389-J081-105, E7389-E044-108, E7389-E044-109, and E7389-E044-110.

In general, the pharmacokinetics (PK) of eribulin is characterized by a rapid distribution phase, with a prolonged elimination phase after intravenous (IV) infusion. The disposition of eribulin follows linear kinetics over the dose range studied, as shown by consistent dose independent PK parameters ( $t_{1/2}$ , clearance [CL], volume of distribution at steady state [ $V_{ss}$ ]) and similar dose-normalized parameters ( $C_{max}/Dose$ ,  $AUC_{0-t}/Dose$  and  $AUC_{0-\infty}/Dose$ ) between eribulin doses ranging from 0.25 to 1.4 mg/m^2 (E7389-A001-101) and from 0.25 to 4.0 mg/m^2 (E7389-A001-102).

Eribulin demonstrated activity across all identified subgroups of subjects, including subjects with advanced/metastatic breast cancer (MBC) (E7389-A001-201, E7389-J081-221 and E7389-G000-211), advanced/metastatic hormone-refractory prostate cancer (E7389-G000-204), or non-small cell lung cancer (NSCLC) (E7389-A001-202). The response rate, clinical benefit rate (CBR) and PFS were reported across breast cancer phenotypes. Eribulin demonstrated activity in subjects with heavily pretreated MBC who were refractory to anti-cancer therapy, including anthracyclines, taxanes, and/or capecitabine.(14)

Results of an Eisai-sponsored, Phase 2 study conducted by the European Organisation for Research and Treatment of Cancer (EORTC) in advanced STS was reported at the annual conference of the American Society of Clinical Oncology (ASCO) in 2010.(15) These results have since been published.(16) Patients with histological proven advanced STS of high or

intermediate grade with disease progression within 6 months prior to study entry and no more than one prior combination regimen, or two prior single agents for advanced STS, was treated with eribulin 1.4 mg/m^2 on Days 1 and 8, every 21 days in four STS strata: adipocytic sarcoma (ADI), leiomyosarcoma (LMS), synovial sarcoma, and other types of sarcoma. The primary endpoint was progression-free rate at Week 12 (PFR12wks).

The PFR12wks was 46.9% (95% CI, 29.9 - 62.8) for ADI sarcoma, 44.7% (95% CI, 28.7 - 59.6) for LMS, 31.6% (95% CI, 12.9 - 52.3) for synovial sarcoma and 24% (95% CI, 9.8 - 41.7) in other types of sarcoma. **Error! Reference source not found.**

[figure not shown]

Figure 1 Protocol E7389-E044-207: Proportion Progression-Free

The median PFS for LMS was 2.9 months (95 % CI, 2.4 - 4.6), the OS at 6 months (Figure ) from the start of treatment (OS6mths) 86.8% (95% CI, 71.2 - 94.3). The median PFS for ADI sarcoma was 2.6 months (95% CI, 1.7 - 6.2), the OS6mths 74.6% (95% CI, 55.5 - 86.4). The median PFS for synovial sarcoma was 2.6 months (95% CI, 2.3 - 4.3), the OS6mths 71.1% (95% CI, 43.7 - 86.8). The median PFS for other types of sarcoma was 2.1 months (95% CI, 1.4 - 2.9), the OS6mths 52.9% (95% CI, 31.2 - 70.7). Responses included complete response ([CR], one subject in the ADI stratum) and partial responses ([PR], one subject each in ADI, synovial and other type of sarcoma strata).

[figure not shown]

Figure 2 Protocol E7389-E044-207: Overall Survival

The most frequent adverse events (AEs) in the EORTC study were hematologic, with Common Terminology Criteria for Adverse Events (CTCAE) Grade 3 or 4 leukopenia reported in 34.6%, neutropenia reported in 51.9% and anemia reported in 7.1% of subjects, respectively. CTCAE Grade 3 or 4 non-hematologic AEs occurred relatively rarely, with fatigue being the most common (7.1%). CTCAE Grade 3 (and no Grade 4) sensory neuropathy was reported in 3.1% of the subjects. Eribulin was associated with manageable tolerability in subjects with STS.

In addition to these completed clinical studies, a program of two Phase 3 studies in advanced, refractory breast cancer has been undertaken. As of 30 June 2010 enrollment is complete in Study E7389-G000-301 and Study E7389-G000-305.

Study E7389-G000-301 results have since been published. The Phase 3 Eisai Study 301(17) compared eribulin mesylate versus capecitabine monotherapy in patients with locally advanced or metastatic breast cancer. The subject population was predominantly HER2/neu negative (68.5%) and second-line MBC (52%; first- and third-line subjects were also included). Exploratory efficacy subgroup analysis showed that HER2/neu negative subjects had an increased overall survival (OS) of 2.4 months (median OS of 15.9 months for eribulin mesylate and 13.5 months for capecitabine; nominal  $P = 0.0299$ ). However, PFS (4 months) and ORR (9.9%) by independent review for eribulin mesylate were similar to the control treatment group (E7389-G000-301 Clinical Study Report).

Study E7389-G000-305 is a Phase 3, open-label, randomized, multicenter study comparing the OS in heavily pretreated subjects with locally recurrent or MBC who have received two to five prior chemotherapeutic regimens ( $\geq 2$  regimens for advanced disease), including an anthracycline and a taxane (unless contraindicated), when treated with Eribulin or treatment of physician's choice. The primary analysis has been completed and reported at the ASCO conference in 2010 and the results have since been published.(14) The study met its primary endpoint with a statistically significant improvement in OS by a median of 2.5 months in the Eribulin arm. Eribulin demonstrated a manageable tolerability profile in this late-line setting.

Please refer to the Investigator's Brochure for further details.

